#### 14.2. Investigator Responsibilities

The Principal Investigator of an investigational site is responsible for ensuring that the study is conducted in accordance with the Clinical Trial Agreement, the protocol, ISO 14155, ethical principles that have their origins in the Declaration of Helsinki, any conditions of approval imposed by the reviewing IRB/EC, and prevailing local and/or country laws and/or regulations, whichever affords the greater protection to the subject.

The Principal Investigator's responsibilities include, but are not limited to, the following.

- Prior to beginning the study, sign the Clinical Trial Agreement and comply with the Investigator responsibilities as described in such Agreement.
- Prior to beginning the study, sign the Protocol Signature page documenting his/her agreement to conduct the study in accordance with the protocol.
- Provide his/her qualifications and experience to assume responsibility for the proper conduct of the study and that of key members of the site team through up-to-date

curriculum vitae or other relevant documentation and disclose potential conflicts of interest, including financial, that may interfere with the conduct of the clinical study or interpretation of results.

- Make no changes in, or deviate from this protocol, except to protect the life and physical well-being of a subject in an emergency; document and explain any deviation from the approved protocol that occurred during the course of the clinical investigation.
- Create and maintain source documents throughout the clinical study and ensure their availability with direct access during monitoring visits or audits; ensure that all clinical-investigation-related records are retained per requirements.
- Ensure the accuracy, completeness, legibility, and timeliness of the data reported to the Sponsor in the CRFs and in all required reports.
- Record, report (Sponsor, IRB/EC as applicable), and assess the relationship and seriousness of adverse events to the device and procedure, as applicable per the protocol.
- Record and report (Sponsor, IRB/EC as applicable) all device deficiencies.
- Report to Sponsor, per the protocol requirements, all Serious Adverse Events (SAEs) and device deficiencies that could have led to a Serious Adverse Device Effect (SADE) and potential/Unanticipated Serious Adverse Device Effect (USADE) or Unanticipated Adverse Device Effect (UADE).
- Report to the IRB/EC and regulatory authorities any SAEs and device deficiencies that could have led to a SADE and potential/USADE or UADE, if required by the national regulations or this protocol or by the IRB/EC, and supply WAE Medical with any additional requested information related to the safety reporting of a particular event.
- Maintain the device accountability records and control of the device, ensuring that the study device is used only by authorized/designated users and in accordance with this protocol and instructions/directions for use.
- Allow the Sponsor to perform monitoring and auditing activities and be accessible to the clinical research monitor or auditor and respond to questions during monitoring visits or audit(s).
- Allow and support regulatory authorities and the IRB/EC when performing auditing activities.
- Ensure that informed consent is obtained from all subjects in accordance with applicable laws, this protocol and local IRB/EC requirements.
- Provide adequate medical care to a subject during and after a subject's participation in a clinical study in the case of adverse events, as described in the ICF.
- Inform the subject of the nature and possible cause of any adverse events experienced.
- As applicable, provide the subject with necessary instructions on proper use, handling, storage, and return of the study device when it is used/operated by the subject.

- Inform the subject of any new significant findings occurring during the clinical investigation, including the need for additional medical care that may be required.
- Provide the subject with well-defined procedures for possible emergency situations related to the clinical study, and make the necessary arrangements for emergency treatment, including decoding procedures for blinded/masked clinical investigations, as needed.
- Ensure that clinical medical records are clearly marked to indicate that the subject is enrolled in this clinical study.
- Ensure that, if appropriate, subjects enrolled in the clinical investigation are provided with some means of showing their participation in the clinical investigation, together with identification and compliance information for concomitant treatment measures (contact address and telephone numbers shall be provided).
- Inform, with the subject's approval or when required by national regulations, the subject's personal physician about the subject's participation in the clinical investigation.
- Make all reasonable efforts to ascertain the reason(s) for a subject's premature withdrawal from clinical investigation while fully respecting the subject's rights.
- Ensure that an adequate investigation site team and facilities exist and are maintained and documented during the clinical investigation.
- Ensure that maintenance and calibration of the equipment relevant for the assessment of the clinical investigation is appropriately performed and documented, where applicable.

## 14.2.1. Delegation of Authority

When specific tasks are delegated by an Investigator, including but not limited to conducting the informed consent process, the Principal Investigator is responsible for providing appropriate training and adequate supervision of those to whom tasks are delegated. The Investigator is accountable for regulatory violations resulting from failure to adequately supervise the conduct of the clinical study.

#### 14.3. Institutional Review Board/Ethics Committee

The protocol and ICF must have the approval of a properly constituted committee ("Institutional Review Board" / "Ethics Committee") responsible for approving clinical trials. The signed IRB/EC approval letter must identify the documents approved (i.e., list the Investigator 's name, the protocol title, and date of approval, and informed consent document). A copy of the approval of the protocol (or permission to conduct the study) and ICF, must be received by the Sponsor before recruitment of subjects into the study and shipment of investigational product/equipment. Prior approval must also be obtained for other materials related to subject recruitment or which will be provided to the subject.

Annual IRB/EC approval and renewals will be obtained throughout the duration of the study as required by local/country or IRB/EC requirements. Copies of the Investigator's reports and the IRB/EC continuance of approval must be provided to the Sponsor.

#### 14.4. Sponsor Responsibilities

- As the study Sponsor, WAE Medical, Inc. is responsible for the overall conduct and quality of the study, including the assurance that the study complies with the appropriate standards and regulations that apply to medical device clinical investigations. WAE Medical will also ensure adherence to the Sponsor general duties as outlined by GCP standards, the US FDA, and as required pertinent individual country laws and regulations. Additionally, the WAE Medical study management will ensure that qualified monitors are monitoring the study according to the protocol, GCP standards and study regulations, and that the Informed Consent process is followed per each site's local and US FDA requirements.
- WAE Medical will ensure the study is registered at a minimum on clinicaltrials.gov as per applicable regulations.
- WAE Medical will select qualified and experienced Investigators and clinical sites to participate in the study and will obtain financial disclosure of participating Investigators.
- The Sponsor will ensure all Investigators and clinical study staff are trained to the study protocol, applicable study specific documentation, and other study specific requirements. Documentation of training will be maintained.
- WAE Medical will select or designate clinical monitors who are qualified by training and experience, to monitor and oversee the conduct of the study.
- WAE Medical will ensure all information and data received regarding study subjects or their participation in this study is kept confidential. Only authorized WAE Medical personnel or an WAE Medical representative including, but not limited to, monitors and a Contract Research Organization (CRO) will have access to these confidential records. WAE Medical may have access to a subject's identifiable health information but will keep this information confidential in accordance with all applicable laws and regulations. WAE Medical may use subjects' health information to conduct this research, as well as for additional purposes, such as overseeing and improving the performance of its device, new medical research and proposals for developing new medical products or procedures, and other business purposes. Information received during the study will not be used to market to subjects; subject names will not be placed on any mailing lists or sold to anyone for marketing purposes.
- Sponsor or CRO representative may request access to all study records, including source documents, for inspection and duplication. In the event that an Investigator is contacted by a regulatory agency or local IRB in relation to this study, the Investigator will notify the Sponsor or designated monitor/CRO as soon as possible. Authorized regulatory personnel have the right to inspect and copy all records pertinent to this study.
- Study data collected during this study may be used by WAE Medical for the purposes of this study, publication, and to support future research and/or other business purposes. All data used in the analysis and reporting of this study will be without identifiable reference to specific subject name.

- The Sponsor will maintain records of the clinical study for a minimum of 2 years after the final study report is completed, or longer if required by local or national regulatory agencies.
- The Sponsor will ensure safety reporting to regulatory authorities, as appropriate, according to local/country specific regulations.
- WAE Medical will ensure a final study report is provided to all IRBs/ECs and regulatory authorities (as applicable).

#### 14.4.1. Role of WAE Medical Representatives in Procedures

WAE Medical personnel can provide technical support to the Investigator and other health care personnel (collectively HCP) as needed during an Poseidon Device procedure. Support may include HCP training, product troubleshooting, addressing HCP questions, or providing clarifications to HCPs concerning the operation of WAE Medical equipment/devices.

In addition, WAE Medical personnel may perform certain activities to ensure study quality. These activities may include the following.

- Observing procedures to provide information relevant to protocol compliance
- Reviewing collected data and study documentation for completeness and accuracy

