# 9. Statistical Considerations

#### 9.1. Endpoints

#### 9.1.1. Primary Endpoint

The Primary Endpoint for this study is the assessment that the PoseidonTM System meets all acceptance criteria for design validation.

- f. User is able to operate device per the instructions for use. This criterion will be assessed in a pass/fail manner with an allowance of only 1 failure in the first 15 subjects and 1 failure in the second 15 subjects (if applicable).
- g. User shall not adversely influence typical actuation of a scope during colonoscopy procedure as assessed using a 5-point Likert scale.
- h. User assessment of functional acceptability of Poseidon device ratchet location as assessed using a 5-point Likert scale.
- i. User assessment of functional acceptability of Poseidon device intergluteal cleft fit as assessed using a 5-point Likert scale
- j. The Poseidon System shall minimize passage of fluids through and around the scope lumen when a scope is in the device, as assessed using a 5-point Likert scale.

To assess whether the Primary Endpoint is met in each group of 15 subjects (as applicable), Criteria A-E must all pass receive a passing score. The questionnaire attached in Appendix A will be answer during each case to document performance of the Poseidon System relative to Criteria A-E

As defined above, criterion A will be assessed on a pass/fail basis. Only 1 failure in each group of 15 will be allowed; >1 failure will result in failure of criterion A.

Criteria B – E will be assessed using a Likert-scale. After 15 each criterion has been assessed in all subjects, scores will be compiled by calculating a mean Likert-score. To pass, each criterion must have a mean Likert score of >3. A score  $\leq$  3 is considered a failure. The rating of the Likert scale will be as follows:

- A value of 1 = Strongly Disagree
- A value of 2 = Disagree
- A value of 3 = Neutral
- A value of 4 = Agree
- A value of 5 = Strongly Agree

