#### 9.4. Data Analyses

To assess whether the Primary Endpoint is met in each group of 15 subjects (as applicable), Criteria A-E must all pass receive a passing score. The questionnaire attached in Appendix A will be answer during each case to document performance of the Poseidon System relative to Criteria A-E

As defined above, criterion A will be assessed on a pass/fail basis. Only 1 failure in each group of 15 will be allowed; >1 failure will result in failure of criterion A.

Criteria B – E will be assessed using a Likert-scale. After 15 each criterion has been assessed in all subjects, scores will be compiled by calculating a mean Likert-score. To pass, each criterion must have a mean Likert score of >3. A score  $\leq$  3 is considered a failure. The rating of the Likert scale will be as follows:

- A value of 1 = Strongly Disagree
- A value of 2 = Disagree
- A value of 3 = Neutral
- A value of 4 =Agree
- A value of 5 = Strongly Agree

Secondary Endpoints will be analyzed as follows:

- 1. Safety: All adverse events will be collected and assessed for relationship to the study device and/or study procedure, seriousness, and severity. Adverse events will be grouped by type and presented in frequencies. If >2 device related SAEs occur, the endpoint will fail.
- 2. Overall Procedure Time: The mean of all procedure times will be taken. There are no pass/fail criteria for this endpoint.
- 3. Device Deficiencies: All device deficiencies will be collected, grouped by type, relationship to adverse events, and presented in frequencies. There are no pass/fail criteria for this endpoint.

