#### WAE Medical personnel will not do the following.

- Practice medicine
- Provide medical diagnosis or treatment to subjects
- Make suggestions or offer opinions regarding the manner in which the Investigator or site staff performs or should not perform any particular aspect of the study procedure, other than ensuring that the device is being used appropriately and safely
- Discuss a subject's condition or treatment with a subject without the approval and presence of the Investigator
- Independently collect critical study data (defined as primary or secondary endpoint data)
- Enter data in EDC systems or on paper CRFs

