#### 16.2. Risk Minimization Actions

All efforts will be made to minimize these potential risks by:

- Selection of qualified Investigators and qualified investigational centers;
- Training the Investigators on proper technique for the Poseidon Device;
- Training the Investigators and on adherence to the study protocol and system IFU;
- Observation of procedures by the WAE Medical, Inc. and/or clinical personnel, as needed;

- Defining clear inclusion/exclusion criteria that ensure only appropriate subjects are enrolled and treated;
- Scheduled monitoring visits to the investigational site; and
- Regular communication with Investigator(s) and staff.

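### Sponsor staff may be in the room when users give the open-label B–E ratings, and nothing keeps them away at that moment; this matters if a criterion's true mean lies near the pass line of 3

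*Combined protocol and SAP*

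**What the plan says.** **Presence.** Section 14.4.1 states: "WAE Medical personnel can provide technical support to the Investigator and other health care personnel (collectively HCP) as needed during an Poseidon Device procedure". It also permits "Observing procedures to provide information relevant to protocol compliance". Section 16.2 lists as a risk-minimization action: "Observation of procedures by the WAE Medical, Inc. and/or clinical personnel, as needed".

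**Review.** Section 14.4.1 permits "Reviewing collected data and study documentation for completeness and accuracy". It does not name the questionnaire. Section 14.4 adds that the sponsor or CRO may request access to all study records.

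**Timing of the rating.** Section 9.1.1 says: "The questionnaire attached in Appendix A will be answer during each case to document performance of the Poseidon System relative to Criteria A-E". Section 9.4 and the synopsis say the same.

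**Limits on sponsor staff.** The list of exclusions that closes 14.4.1 bars them from independently collecting primary or secondary endpoint data. They also may not "Enter data in EDC systems or on paper CRFs", or give opinions on how the procedure is performed beyond appropriate and safe use of the device. Section 10.1 provides an audit trail, an Investigator signature on the eCRF, and a new signature for changes to submitted data.

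**Decision rule.** Each of B–E passes if its mean 5-point score exceeds 3 (sections 4.1, 9.1.1, 9.4). All of A–E and Secondary Endpoint 1 must pass. A pass in the first 15 subjects ends the study; a failure leads to design changes and a second group of 15 (section 9.5).

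**The concern.** Four of the five primary criteria are opinions of the user, who knows which device is being rated. Every subject receives the device (section 5.2), and no masked or independent rater is described. The people who may be standing by work for the party with a stake in the result.

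The existing limits govern who writes the score down and what happens to it after submission. They do not govern the conditions under which the user forms and gives it. A user who rates a little more kindly in company would shift every attended case in the same direction, and such a shift does not average out over 15 cases. With a pass line just above Neutral, it could carry a marginal criterion over. This is separate from how an assisted case should be scored under criterion A.

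**Working it through.** The documents give no power, alpha, expected mean or planning SD for B–E, so there is no figure of theirs to reproduce. The check asks how much a small systematic shift would move the pass probability.

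**Inputs**
- Ratings per criterion per group: n = 15 (section 5.1).
- Pass rule: mean > 3 on integer scores 1 to 5 (section 9.1.1).
- SD of a rating: not given. Assumed 1.0, with 0.7 and 1.2 as the range.
- True mean before any shift: not given. Values from 2.8 to 4.0 are shown.
- Size of the shift: an assumption, taken as 0.3.
- Ratings are treated as independent. With one or two sites there are probably few raters, so ratings may be correlated and the true standard error larger.

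**Step 1: the threshold in whole ratings.** The highest failing total is 45 (45/15 = 3.000). The lowest passing total is 46 (46/15 = 3.067). One rating raised by one point can therefore flip a criterion sitting at 45. A shift of 0.2 equals 0.2 × 15 = 3 ratings raised by one point; a shift of 0.3 equals 4.5.

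**Step 2: standard error.** SE = SD/√15, which is 0.18, 0.26 and 0.31 for SD 0.7, 1.0 and 1.2. A shift of 0.3 is about one SE.

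**Step 3: pass probability for one criterion.** P(total ≥ 46) comes from the exact distribution of the sum of 15 ratings, using a discrete 1–5 distribution with the stated mean and SD. A normal approximation with continuity correction, 1 − Φ((45.5/15 − μ)/(SD/√15)), agrees to within 0.3 percentage points. For example, with μ = 2.8 and SD 1.0: 1 − Φ((3.033 − 2.8)/0.258) = 1 − Φ(0.904) = 0.183.

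| True mean | SD 0.7: no shift → +0.3 | SD 1.0: no shift → +0.3 | SD 1.2: no shift → +0.3 |
|---|---|---|---|
| 2.8 | 9.7% → 64.5% | 18.3% → 60.2% | 22.6% → 58.6% |
| 3.0 | 42.6% → 93.1% | 44.9% → 84.9% | 45.7% → 80.5% |
| 3.2 | 82.3% → 99.5% | 74.1% → 96.3% | 70.5% → 93.1% |
| 3.5 | 99.5% → 100% | 96.3% → 99.8% | 93.1% → 99.1% |
| 4.0 | 100% → 100% | 100% → 100% | 99.8% → 100% |

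Omitting the continuity correction overstates these figures by about 3 to 5 points. At SD 1.0 and μ = 2.8, for instance, it gives 21.9% instead of 18.3%.

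**Step 4: all four Likert criteria together.** If B–E were independent and shared one true mean, with SD 1.0, the joint pass probability is the fourth power of the single value. A shift of 0.3 then moves it from 0.1% to 13% at a mean of 2.8, from 4% to 52% at 3.0, and from 86% to 99% at 3.5.

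**Step 5: could a comparison by attendance detect such a shift?** With a 7/8 split and SD 1.0, the SE of the difference is √(1/7 + 1/8) = 0.52. The 95% half-width is 2.16 × 0.52 ≈ 1.1 (t, 13 df). A shift of 0.2 to 0.5 would not be visible.

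**The case against.** The best case against the point is that this is an unpowered, descriptive design-validation study in which sponsor support is openly declared. Controls also exist: sponsor staff cannot collect or enter endpoint data, the eCRF is signed and audited, and investigators disclose financial and other conflicts (sections 14.2 and 14.4). No bias is shown, and its size is assumed. Users would still know the device and know that the sponsor receives their scores, so an empty room removes only part of any courtesy effect.

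Much of this stands, and it rules out several stronger readings that a reader might infer:

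- *Sponsor staff could record or alter scores.* The exclusions in 14.4.1 and the controls in 10.1 speak against this.
- *The plan says sponsor staff review the questionnaire.* It does not. The review line is an ordinary quality check on collected data, and extending it to Appendix A before signature is an inference. Presence during the case is the firmer ground.
- *Sponsor attendance goes unrecorded.* Only its absence from Table 1 in section 8.1 and from the list in section 8.4.2 can be stated; the eCRFs are not in the text available for review.
- *A few tenths of a point decide the study.* That is true of one criterion only when its true mean is near 3. The overall result also needs every other criterion and Secondary Endpoint 1 to pass.

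The gap itself remains: no sentence protects the moment of rating, and closing it does not touch device support.

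**Conclusion.** The point holds as a gap in the plan that is cheap to close. Sponsor personnel may be present when open-label primary ratings are given and may, by inference, see them before signature; the existing safeguards cover neither. Whether bias would occur, and how large it would be, cannot be shown from the documents.

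The consequence is conditional. A shift of 0.3 adds about 35 to 55 percentage points to one criterion's pass probability if its true mean is 2.8 to 3.0, at most about 6 points at 3.5, and essentially none at 4.0. These figures rest on an assumed SD of 0.7 to 1.2, independent ratings and a uniform shift. Since the plan gives no expected mean, a near-threshold result can be neither excluded nor presumed. The documents do not support calling the study invalid or its ratings biased.

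**What to change.** In sections 14.4.1, 9.1.1 and 9.4 and in the synopsis, state that the user completes and signs Appendix A immediately after scope-out, without sponsor personnel present, and that sponsor personnel do not see it until it is signed in the EDC. Replace the present during-the-case timing in all of these places so that they agree. Sponsor support and observation during the procedure, including the observation listed in section 16.2, stay as written.

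Optionally, add one eCRF field for sponsor attendance (yes/no) and show it as a descriptive listing only. It should not be presented as a test for bias: 15 cases are too few, and because attendance is as needed it may follow case difficulty or the learning curve.

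Cost: protocol wording and, if wanted, one field. The form is completed just after the case rather than during it, and completeness queries come slightly later through the EDC. Sample size and threshold do not change.
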